3.2 General study level definitions

3.2.1 First and last dose of study treatment

For each participant the start of study treatment is defined as the date and time of the first dose of UCB6114. This will be considered as the starting point of the combination therapy.

Note that TFD/TPI is taken by the participant at home prior to attending the clinic for the infusion of UCB6114 on C1D1.

Similarly, for each participant, the last dose of study treatment will be the date of the last dose of UCB6114.

3.2.2 Relative day and time

For each participant, the relative day of an event or assessment will be derived using the date of their first dose of UCB6114 as reference.

Relative days for an event or assessment occurring before the date of first dose of UCB6114 are calculated as follows:

$$\text{Relative Day} = \text{Event/Assessment Date} - \text{Date of First Dose of UCB6114}$$

The relative day for an event or assessment occurring on the date of first dose of UCB6114 is 1. The relative day for an event or assessment occurring on or after the first dose of UCB6114 to the date of the last dose of UCB6114 will be calculated as follows:

$$\text{Relative Day} = (\text{Event/Assessment Date} - \text{Date of First Dose of UCB6114}) + 1$$

For events or assessments occurring after the date of the last dose of UCB6114, relative day will be prefixed with ‘+’ in the data listings and will be calculated as follows:

$$\text{Relative Day} = \text{Event/Assessment Date} - \text{Date of Last Dose of UCB6114}$$

There is no relative Day 0. Relative day will not be calculated in cases where dates are partial and should be presented as “--” in the relevant data listing.

Relative time of TEAEs recorded on, but not limited to, the day of UCB6114 infusion (Days 1 and 15 of each cycle) will be derived in minutes as follows using the infusion start time as reference:

$$\text{Relative Time of TEAE} = \text{Onset Time of TEAE} - \text{Start Time of UCB6114 Infusion}$$

Relative times of PK and PD sampling will be derived in hours using the end of UCB6114 infusion time on the day of dosing as reference, i.e. on Days 1 and 15 of each cycle:

$$\text{Relative Sampling Time} = \text{Sampling Time} - \text{End Time of UCB6114 Infusion}$$

3.2.3 Study periods

Part B of the study will consist of the following study periods:

- Screening Period – up to 28 days;
- Treatment Period – Successive 28-day cycles of study treatment (UCB6114 will be administered as an iv Q2W dose on Day 1 and Day 15 of each cycle and TFD/TPI will be

administered [bid] within 1 hour of completion of morning and evening meals at home on Days 1 to 5 and Days 8 to 12, continuing until disease progression, unmanageable toxicity, or participant withdrawal). Within the first cycle of the Treatment Period, a 28-day DLT Observation Period is defined to determine safety events for dose escalation decisions using mTPI;

- Safety Follow-up Period – up to 30 days after the last dose of UCB6114.

There will be a further extended follow-up period, up to 3 months after the last dose of UCB6114, at which time the Final Visit will be performed.

For each participant, the end of the Treatment Period is defined by the date of their last dose of UCB6114.

The end of Part B of the study is defined by the date of the Final Visit for the last participant (3 months after the last participant's last dose of UCB6114), or the date of the SFU visit, if they discontinue prior to attending the Final Visit, or their last contact date if they discontinue early from the study without attending the SFU visit.

3.2.4 Visits

Unless otherwise specified, in the TFLs, visits will be labelled as follows (as applicable) using timepoints as recorded in the database:

Screening
Baseline
Cycle 1, Day X
Cycle 2, Day X
Cycle 3, Day X
Cycle 4, Day X
Cycle X, Day X
Etc.
SFU
Final Visit

3.3 Definition of Baseline values

Baseline in Part B will be the last available value prior to the first dose of UCB6114. Both scheduled and unscheduled values, as well as any repeated values, should be used when defining Baseline.

Measurement-specific Baseline definitions are presented in [Table 3-1](#).

Table 3-1: Definition of Baseline

Measurement	Definition of Baseline
Echocardiogram (LVEF) Tumor assessments (antitumor activity)	Screening value
12-lead ECG Physical examination and weight Vital signs Clinical laboratory data ECOG performance status	Predose value obtained on Cycle 1, Day 1, or, if missing, Screening value
Serum and urinary markers of bone turnover Circulating gremlin-1 (cGremlin-1) Immunogenicity (ADA)	Predose sample value obtained on Cycle 1, Day 1

ADA=anti-drug (UCB6114) antibody; ECG=electrocardiogram; ECOG=Eastern Cooperative Oncology Group; LVEF=left ventricular ejection fraction.

3.4 Protocol deviations

Per ICH definition, important protocol deviations (IPDs) are a subset of protocol deviations that may significantly impact the completeness, accuracy, and/or reliability of the study data or that may significantly affect a participant's rights, safety, or well-being. The criteria for identifying potentially important protocol deviations will be defined within the IPD specifications document.

For Part B of this study, IPDs will be categorized as follows:

- Inclusion/exclusion criteria deviations
- Incorrect treatment or dose administered
- Procedural non-compliance
- Prohibited concomitant medication use (see Section 6.5.5 of the protocol)
- Withdrawal criteria deviation

All protocol deviations will be reviewed as part of the ongoing data cleaning process and Data Evaluation Meetings (DEMs), and decisions made on whether they should be considered important or not, and whether they warrant a participant's exclusion from an analysis set, or partial exclusion from an analysis due to being an IPD (e.g. prohibited concomitant medication use). Multiple DEMs will be scheduled prior to the final database lock for Part B, in line with regulatory safety reporting requirements, with the final one held after all data have been verified/coded/entered into the database.

More specifically, participants who have IPDs relating to dosing of study treatment (e.g. interrupted, discontinued and missed infusion, incomplete/incorrect dose administered, additional dose received, or infusions administered outside of the defined visit window) will be reviewed at the DEM for potential exclusion of UCB6114 concentration data from the by-visit summaries at an individual visit or from the visit at which the dosing deviation was observed onwards.

Any protocol deviations that are considered related to coronavirus disease 2019 (COVID-19) will be reviewed on an ongoing basis in case they collectively or individually give reason to consider a protocol amendment (e.g. study design changes or changes to primary analysis methods etc.). To facilitate this ongoing review, protocol deviations will be categorized as ‘related to COVID-19’ within the Clinical Trial Management System (CTMS) (ICOTrial). The COVID-19-related IPDs will then be listed separately for review and discussion at the DEMs.

3.5 Analysis sets

3.5.1 Enrolled Set (ES)

The Enrolled Set (ES) consists of all study participants who sign the Informed Consent Form.

This analysis set includes screening failures and will be used for the summary of disposition of study participants and for selected data listings (which will include all available data for the screening failures).

3.5.2 Safety Analysis Set (SS)

The Safety Analysis Set (SS) consists of all study participants who receive at least 1 full or partial dose of UCB6114.

This analysis set will be used for the reporting of demographic, baseline characteristics, safety and immunogenicity data. All summaries of the exploratory antitumor activity endpoints will be repeated for the SS as a sensitivity analysis.

3.5.3 Per-protocol Set (PPS)

The Per-protocol Set (PPS) consists of all study participants in the SS who do not have IPDs that may substantially affect antitumor activity. Potential exclusions will be reviewed at the DEMs and a final determination of the composition of this analysis set will be made prior to the final database lock for Part B.

The PPS will be the primary analysis set for the analysis of the exploratory antitumor activity endpoints.

3.5.4 Pharmacokinetic Set (PKS)

The Pharmacokinetic Set (PKS) consists of all study participants in the SS who have at least 1 evaluable postdose UCB6114 concentration sample (i.e. a sample which is above the lower limit of quantitation and for which the date and time of the sample and prior date and time of dosing are known). Additional participants or specific samples may be excluded from the PKS at the discretion of the Advanced Modeling and Simulation scientist/Quantitative Clinical Pharmacologist at UCB.

Pharmacokinetic analysis will be performed for the PKS.

3.5.5 Anti-drug Antibody Set (ADAS)

The Anti-drug Antibody Set (ADAS) consists of all study participants in the SS who have at least 1 evaluable ADA assessment.

Immunogenicity analyses will be performed for the ADAS.

3.5.6 Pharmacodynamic Set (PDS)

The Pharmacodynamic Set (PDS) consists of all study participants in the SS who have at least 1 evaluable PD assessment (where appropriate, the sample should be above the lower limit of quantitation and the date and time of the sample should be known).

Pharmacodynamic analysis will be performed for the PDS.

3.5.7 DLT Evaluable Set (DES)

The DLT Evaluable Set (DES) will include all study participants who, during the 28-day DLT assessment period receive the planned dose of UCB6114 and at least 80% of the planned dose of TFD/TPI or stopped treatment due to DLT.

The DES will be used by the SMC for all dose escalation/de-escalation decision making.

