Part B will be undertaken using the modified toxicity probability interval (mTPI) method. The mTPI design uses a Bayesian decision framework to inform dose-escalation and dose de-escalation decisions. A target DLT rate of 25% with an equivalence interval (20% to 30%) will be used to estimate the maximum tolerated dose (MTD) of the combination regimen during dose escalation. For all UCB6114 dose levels, enrolled participants will be treated in cohorts of 2 to 4 participants (target of 3), who can be treated in parallel. Each UCB6114 dose level may have more than one cohort and will have a minimum of 3 and a maximum of 9 evaluable participants. For further detail on the mTPI method, the calculated model-based dose-escalation/dose de-escalation decisions to help inform the Safety Monitoring Committee (SMC)'s decision, and the determination of the MTD, please refer to Section 4.1.3.2.2 of the protocol. Detail on the operating characteristics for the mTPI design is included in [Section 2.4](#) below.

[figure not shown]
The planned duration of study treatment during Part B is 2 cycles. Participants may remain on study for additional cycles if they are receiving therapeutic benefit or until they fulfill one of the criteria for study discontinuation. Participants will continue treatment until disease progression, unmanageable toxicity, or withdrawal of consent. Upon discontinuation of treatment, participants will be referred to appropriate follow-up care per the investigator's judgment.

From Part B, a recommended Phase 2 dose for UCB6114 in combination with TFD/TPI (RP2D-T) will be determined based upon the totality of information, including the safety profile, PK data, PD biomarker data, and available antitumor activity.

Part B of the study is planned to be conducted at study sites in the United Kingdom (UK) and United States (US).

A schematic diagram of Part B of the study is provided in [Figure 2-1](#).

Figure 2-1: Study Schematic for Part B

bid=twice daily; D=Day; DLT=dose-limiting toxicity; iv=intravenous; mTPI= modified toxicity probability interval; po=oral; TFD/TPI=trifluridine/tipiracil

*Dose must not exceed 80mg/dose

Notes: A dose may be given in more than 1 cohort

Escalation to the next dose level or de-escalation to the previous dose level will be guided by the mTPI algorithm.

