A Study Steering Committee (SSC) will be implemented prior to the start of Part B. In consultation with the SMC, the SSC will recommend to the Sponsor the dose and dosing regimen to be taken forward for Part B. Part B of ONC001 is planned to be initiated after Cohort 3 of Part A has completed the 28-day DLT assessment period, after consultation with the SMC, and when the SCC has provided a recommendation to dose escalate to the next protocol-defined level in Part A of the study. The SSC members will include the coordinating investigator, supporting co-investigators, and clinical experts not involved in the study. The medical, scientific, and clinical study expertise of the SSC will assist the Sponsor in identifying and resolving any study related issues, such as study design, study implementation and conduct, and data analysis and reporting.

During the Treatment Period, UCB6114 will be administered as an iv infusion Q2W, while TFD/TPI will be administered orally twice daily (bid) within 1 hour of completion of morning and evening meals at home on Days 1 to 5 and Days 8 to 12 of each 28-day cycle. For the convenience of the participants, TFD/TPI can be administered at home to allow for the 12-hour interval between TFD/TPI doses associated with meals. The starting dose of TFD/TPI in adults is 35mg/m² administered orally bid (total daily dose of 70mg/m²) with dosage calculated for each participant according to body surface area (BSA) (see Table 4-4 of the protocol). The dosage must not exceed 80mg/m² (based on the trifluridine component).

It is expected that up to 3 dose levels of UCB6114 will be explored in combination with the standard TFD/TPI dosing regimen. However, additional dose levels may be added based on emerging data and recommendations of the SMC. Dose escalation steps are currently planned at a maximum of 2-fold. Escalating dose levels in Part B will not exceed a dose level tested and considered safe by the SMC to allow dose escalation in monotherapy (Part A).

Eligible participants who withdraw from the study before receiving study treatment will be replaced. Participants who fail to receive the second planned dose of UCB6114 within 7 days of

the scheduled administration day during the 28-day DLT Observation Period for reasons not related to toxicity will be replaced by a new participant in that cohort. Safety data for replaced participants will be included in the data listings and in the summary tables, as applicable.

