3.5.7 DLT Evaluable Set (DES)

The DLT Evaluable Set (DES) will include all study participants who, during the DLT assessment period receive the planned dose of UCB6114 and at least 80% of the planned dose of mFOLFOX6 or stopped treatment because of a DLT.

The DES will be used by the SMC for all dose escalation/de-escalation decision making.

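### A DLT does not by itself make a participant DLT-evaluable: one who is under-dosed because of a DLT but does not stop treatment drops out of the set used for escalation decisions

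*SAP*

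**What the plan says.** Part B SAP, 3.5.7, gives two routes into the DES. During the 28-day DLT period a participant must "receive the planned dose of UCB6114 and at least 80% of the planned dose of TFD/TPI or stopped treatment due to DLT". Part C SAP, 3.5.7, has the same structure, with the second part reading "at least 80% of the planned dose of mFOLFOX6 or stopped treatment because of a DLT". On use, the text is unqualified: "The DES will be used by the SMC for all dose escalation/de-escalation decision making".

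Related text in both SAPs:

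- Section 8.2 defines a DLT by possible relation to UCB6114, onset in Cycle 1 and criteria held in the protocol. Stopping treatment is not part of the definition as the SAP gives it.
- Section 8.2 also tabulates adverse events leading to interruption or reduction of UCB6114 and of the backbone therapy, separately from those leading to discontinuation.
- Section 2.3 sets a target DLT rate of 25% with a 20% to 30% equivalence interval, cohorts of 2 to 4, and dose levels that, in the Part B wording, "will have a minimum of 3 and a maximum of 9 evaluable participants".
- Section 2.3 says that a treated participant who does not receive the second UCB6114 dose within 7 days of schedule "for reasons not related to toxicity will be replaced by a new participant in that cohort".
- Section 5.1 leaves the DES out of the listing of analysis-set exclusions for the study report.

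**The concern.** In a dose-escalation set the usual logic is asymmetric. A participant with a DLT is informative whatever dose was received; a minimum exposure is needed only to call someone free of DLT. Section 3.5.7 applies the exposure requirement to everyone and relaxes it only for those who stopped treatment. A participant who has a DLT, is reduced or held below threshold and then continues falls between the two routes.

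A DLT is itself a likely cause of under-dosing, so such an exclusion is tied to the outcome being counted. At 3 to 9 evaluable participants per dose level, one DLT more or less can decide between escalating, staying and de-escalating. The replacement text in 2.3 does not settle the matter: it covers a second UCB6114 dose missed for non-toxicity reasons and is silent on a participant who is non-evaluable because of toxicity.

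**Working it through.** **1. Who is dropped under the text.** The rule is (planned UCB6114 and at least 80% of the planned backbone) or (stopped treatment because of a DLT).

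| Participant with a Cycle 1 DLT | Dosing route | Stopping route | In the DES? |
|---|---|---|---|
| Stops treatment because of it | may fail | met | Yes |
| Continues, thresholds still met | met | not met | Yes |
| Dose delayed but given within the period, thresholds met | met | not met | Yes |
| Reduced below a threshold, continues | not met | not met | **No** |
| Held, ends below a threshold, then resumes | not met | depends on whether *stopped* means permanently | **Unclear** |

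Timing narrows the group. TFD/TPI has 10 dosing days (Days 1 to 5 and 8 to 12). By Day 10, 5 + 3 = 8 of the 10 are complete, so a hold from Day 11 after full dosing still leaves 80%. UCB6114 is given on Days 1 and 15. In Part C, section 8.1 lists mFOLFOX6 on Days 1 and 2 and Days 15 and 16. A DLT arising after these doses cannot cause under-dosing in Cycle 1.

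**2. Reproducing the plan's own figures.** The SAP refers the mTPI details to the protocol, so these settings are assumptions: Beta(1,1) prior; exclusion of a dose if Pr(p > 0.25) > 0.95; cohorts of 3, at most 9 per dose; the trial stops if the first cohort at the lowest dose calls for de-escalation. That last event needs at least 2 DLTs in 3, with probability 3p²(1−p) + p³:

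- p = 0.05: 0.73% (Table 2-2: 0.8% in Scenario 1, 0.7% in Scenario 2)
- p = 0.15: 6.1% (Table 2-2: 6.7%)
- p = 0.25: 15.6% (Table 2-2: 15.2%)

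A simulation of 5000 trials per scenario gives every cell of Table 2-2 within 2 percentage points. For Dose 3 it gives 91.8, 59.5, 20.2 and 3.6%, against the stated 91.4, 58.9, 21.6 and 3.8%. The assumed settings are therefore close to those the sponsor used.

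**3. Effect of losing one DLT participant.** With y DLTs in n, the posterior is Beta(1+y, 1+n−y). The unit probability mass (UPM) of an interval is its posterior probability divided by its length. The largest UPM among (0, 0.20), (0.20, 0.30) and (0.30, 1) gives Escalate, Stay or De-escalate.

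Example, 0/3: Pr(p ≤ x) = 1 − (1−x)⁴.

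- Low: (1 − 0.4096)/0.20 = 2.952
- Middle: (0.4096 − 0.2401)/0.10 = 1.695
- High: 0.2401/0.70 = 0.343

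The largest is the low interval, so Escalate.

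| All treated | UPM low / mid / high | Decision | DES after the loss | UPM low / mid / high | Decision |
|---|---|---|---|---|---|
| 1/4 | 1.314 / 2.091 / 0.755 | Stay | 0/3 | 2.952 / 1.695 / 0.343 | Escalate |
| 2/4 | 0.290 / 1.052 / 1.196 | De-escalate | 1/3 | 0.904 / 1.675 / 0.931 | Stay |
| 3/6 | 0.167 / 0.927 / 1.249 | De-escalate | 2/5 | 0.494 / 1.568 / 1.063 | Stay |
| 4/9 | 0.164 / 1.175 / 1.214 | De-escalate | 3/8 | 0.428 / 1.847 / 1.042 | Stay |
| 2/6 | 0.740 / 2.049 / 0.924 | Stay | 1/5 | 1.723 / 2.352 / 0.600 | Stay |

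Over all counts with n from 2 to 9, no loss moved the decision toward de-escalation. Many counts are unchanged, among them 2/5, 2/6, 2/7, 3/7, 3/8 and 3/9.

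**4. Sensitivity to frequency.** Let q be the share of DLT participants who end under-dosed without stopping. The documents give no value, so q is an assumption shown over a range. Percentage of simulated trials selecting Dose 3:

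| q | Scenario 3 (true rate 35%), lost participant not made up / made up | Scenario 4 (true rate 50%), not made up / made up |
|---|---|---|
| 0% | 20.2 | 3.6 |
| 25% | 39.0 / 35.9 | 11.4 / 9.5 |
| 50% | 64.1 / 60.4 | 31.9 / 27.8 |
| 75% | 87.7 / 85.3 | 71.6 / 66.7 |

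The made-up column is nearer to the stated minimum of 3 evaluable participants.

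**The case against.** Several counter-arguments have force.

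- **The affected group is narrow.** A reader might infer that any DLT leading to a hold, reduction or delay removes the participant. The documents do not support that: a delayed dose given within the period, a hold from Day 11 of TFD/TPI, or any DLT arising after the Cycle 1 doses leaves the thresholds met.
- **A hold may count as stopping.** Part B section 8.1.1 and Part C section 8.1 use *stopped* for a temporary interruption and contrast it with permanent discontinuation. For holds the defect is therefore ambiguity. A reduction cannot be read as stopping.
- **The protocol may close the gap.** The DLT criteria and the mTPI decision rules sit there. If it requires stopping after every DLT, the excluded group is empty. The SAP does not say so.
- **The committee sees more than the DES.** Under section 4.5 the SMC reviews cumulative safety data, can adjudicate DLTs and makes the recommendation; mTPI only guides it. This softens the effect but does not correct the count, and 3.5.7 names the DES as the basis for all such decisions.
- **Lost participants can be made up.** A dose level needs at least 3 evaluable participants and may take further cohorts. That restores the number, not the lost DLT. Losing someone below 80% of the backbone for reasons unrelated to toxicity creates no outcome-dependent bias.

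**Conclusion.** Wrong as written. Section 3.5.7 of both SAPs can remove a participant together with the DLT from the set used for all escalation and de-escalation decisions. This is clear for a reduction that leaves the participant below a threshold, and holds for an interruption if *stopped* means permanently. Where it changes the mTPI decision, the shift is toward escalation; at many counts there is no change.

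Two stronger readings are not supported. One is that the DLT rate entering the model is biased downward as a matter of fact: that needs a non-zero share of under-dosed, not-stopped DLT cases, for which the SAP gives no figure. The other is that the reported primary endpoint is distorted: under section 8 safety summaries use the Safety Analysis Set unless otherwise stated, so reported DLT incidence is not affected.

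The individual decisions rest on the assumed Beta(1,1) prior, and the selection percentages also on the other assumed settings and on q. The gap in the wording rests on neither.

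**What to change.** In 3.5.7 of both SAPs, define the DES as:

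- (a) every participant with a DLT in the 28-day DLT Observation Period, whatever amount of UCB6114 or backbone therapy was received; plus
- (b) participants without a DLT who received the planned UCB6114 and at least 80% of the planned TFD/TPI (Part B) or mFOLFOX6 (Part C) in that period.

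This also removes the need to define *stopped* for DES membership. The replacement text in 2.3 of both SAPs summarises the protocol, so it should be reconciled with this definition and with the protocol; no new replacement rule is proposed here.

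The cost is a wording change in each plan and an update of the program that builds the SMC output. No new data are needed. The downside is that the DLT rate used for decisions may be slightly less favourable.
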